4.3 Secondary Endpoints Analyses

4.3.1 Supportive Secondary Endpoints

4.3.1.1 Secondary Endpoints in Efficacy

The secondary endpoints in efficacy listed below will be summarized for MITT by PH type and by age group.

- The percentage of participants with spot urinary oxalate-to-creatinine ratio \leq the ULN or $\leq 1.5 \times$ ULN at any time point through Month 6 will be summarized (n, %).

Statistical Analysis Plan Study ID: NN7022-PHYOX8	CONFIDENTIAL	Date: Jan 19, 2024 Version: 2.0 Status: Final Page: 22 of 29	Novo Nordisk
--	---------------------	---	---------------------

- The percent change from baseline in eGFR at Month 6 (only in participants \geq 12 Months of age at Screening) will be summarized (n, mean, standard deviation, median, minimum, maximum).

4.3.1.2 Secondary Endpoints in Safety

The secondary endpoints in safety are listed below:

- The incidence and nature of TEAEs and SAEs.
- Change from Baseline in 12-lead ECG, physical examination findings, vital sign assessments, and clinical laboratory tests.

All safety analyses will be performed on the SAF population and will be presented by PH type and by age group. All summaries will be descriptive in nature. No statistical comparisons will be performed.

4.3.1.2.1 Adverse Events

All AEs, TEAEs, and SAEs will be coded using the MedDRA v26.0 or higher. AEs will be classified as treatment-emergent for analysis in summary tables where applicable.

An overview summary of AEs, including number of event counts and percentages will be presented for participants with:

- any TEAEs,
- TEAEs related to study intervention,
- TEAEs leading to treatment discontinuation,
- Treatment-emergent SAEs,
- Treatment-emergent SAEs related to study treatment,
- TEAEs of special interest (i.e., injection site reactions; muscle pain or weakness; kidney stone events: renal stone requiring medical intervention, stone passage with or without hematuria, and renal colic requiring medication),
- Fatal TEAEs.

The number of events and number and percentage of participants with AEs will be summarized by SOC and PT. This summary will further be tabulated by strongest relationship to study intervention (related: definitely, probably, and possibly related; unrelated: unrelated; missing). A similar summary of TEAEs will be produced by maximum intensity (mild, moderate, severe, missing).

In addition, the number and percentage of participants who experienced (1) treatment-emergent SAEs; (2) TEAEs leading to study discontinuation; and (3) non-serious TEAEs (all TEAEs except serious TEAEs) that occurred in at least 2 or more participants will be presented by SOC and PT for SAF.

In addition, listings will be provided for TEAEs.

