**Discontinuation from study intervention does not mean discontinuation from the study.**

Remaining visits and study procedures should be completed as indicated by the SoA.

See the SoA for data to be collected at the time of intervention discontinuation and follow-up and for any further evaluations that need to be completed.

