#### 9.4.3.2. Safety Endpoints

All safety analyses will be performed on the Safety Population. The incidence and nature of TEAEs and SAEs, along with change from Baseline in 12-lead ECG, physical examination findings, vital sign assessments, and clinical laboratory tests will be summarized.

Adverse events will be defined as treatment emergent if they have an onset or worsen in severity after a participant receives the study intervention. Treatment-emergent AEs will be summarized by SOC and preferred term according to the MedDRA. Treatment-emergent AEs will be further summarized by severity and relationship to study intervention. Adverse events leading to discontinuation, SAEs, and deaths will be summarized/listed.

Descriptive statistics will be provided for absolute values and changes from baseline in physical examination findings, vital sign measurements, ECGs, and clinical laboratory results at each timepoint.

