1.1.2 Primary Estimand

The primary clinical question of interest is: What is the treatment effect of nedosiran in lowering urinary oxalate excretion (Uox) assessed via percent change from baseline in spot urinary oxalate-to-creatinine ratio at Month 6 in PH1 pediatric participants (birth to 11 years of age) with relatively intact renal function.

For the primary objective, the estimand is defined with five attributes:

- Treatment condition of interest is the monthly nedosiran administration.
- The target population is PH1 pediatric participants (birth to 11 years of age) with relatively intact renal function.
- The endpoint is percent change from baseline at Month 6 in spot urinary oxalate-to-creatinine ratio.
- The intercurrent events (ICEs) include treatment discontinuation for any reasons and will be handled by the treatment policy strategy.

[figure not shown]
Population-level summary is the percent change from baseline at Month 6 estimated by Mixed-effect Model Repeated Measures (MMRM) approach.

Rationale for estimand: The primary estimand assesses the treatment benefit of nedosiran in lowering urinary oxalate-to-creatinine ratio that can be expected in clinical practice, provided that the treatment adherence in the study reflects what would be seen in clinical practice.

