4.1.2 Disposition of Participants and Withdrawals

Disposition will include tabulations for the number of participants screened and screen failed; the number and percentage of participants who: received treatment, completed study, reasons for study discontinuation/withdrawal (overall and by reason for study discontinuation/withdrawal); the number and percentage of participants in each analysis population will also be displayed. All the tabulations will be for SAF and by PH type and age group (0-<2, 2 - < 6, 6-<9, and 9 - 11 years).

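### The SAP's by-term table of discontinuation AEs covers leaving the study only, so AEs that stop nedosiran in children who stay on study are counted but not identified by term or reason

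*SAP*

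**What the plan says.** SAP 4.3.1.2.1 uses two discontinuation events. The overview summary has a row for "TEAEs leading to treatment discontinuation". Later in the same section, the outputs by SOC and PT are treatment-emergent SAEs, "TEAEs leading to study discontinuation", and non-serious TEAEs occurring in at least two participants. The section also plans a general table ("The number of events and number and percentage of participants with AEs will be summarized by SOC and PT") and listings ("In addition, listings will be provided for TEAEs").

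SAP 4.1.2 (disposition) tabulates "reasons for study discontinuation/withdrawal (overall and by reason for study discontinuation/withdrawal"). It has no row for stopping study intervention. SAP 4.6.1 summarizes doses received and the number dosed at each dosing visit, without reasons.

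The protocol separates the two events. Section 7.1.1 requires permanent discontinuation of study intervention for a related SAE (with a stated exception), for defined hepatic changes and for pregnancy, and then says: "Discontinuation from study intervention does not mean discontinuation from the study". Remaining visits are to be completed. The liver appendix (10.6) repeats this for participants aged 6 years and over. Protocol 9.4.3.2 states: "Adverse events leading to discontinuation, SAEs, and deaths will be summarized/listed", without saying which kind of discontinuation is meant. SAP 1.1.2 makes stopping drug the named intercurrent event of the primary estimand: "The intercurrent events (ICEs) include treatment discontinuation for any reasons".

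**The concern.** The overview row and the by-term table look as though the second breaks down the first, but they describe different events. The stopping rules in Protocol 7.1.1 act on the drug, and sites are asked to keep the child in follow-up. The better a site follows that instruction, the fewer drug-stopping AEs reach the by-term discontinuation table.

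The secondary safety endpoint covers both how often TEAEs occur and what they are. For AEs that stop nedosiran, the overview gives the first but not the second. The estimand has a related gap. Under a treatment policy strategy, Month 6 values from children off drug stay in the analysis, and a reader would want to know why those children stopped.

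**Working it through.** The plan gives no figure to reproduce. The check traces four kinds of child through the planned outputs, assuming in each that the triggering finding is recorded as a TEAE.

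- **A.** Drug stopped for a related SAE; child attends to Day 180 (Protocol 7.1.1).
- **B.** Aged 6 or over, hepatic criterion met, event not serious; child stays (Protocol 7.1.1 and 10.6).
- **C.** Under 6, hepatic criterion met, no alternative cause found; Protocol 10.6 has the child leave the study.
- **D.** Under 6, elevation recurs after re-challenge; Protocol 10.6 stops the drug permanently and gives no instruction there to leave the study.

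| Output | A | B | C | D |
|---|---|---|---|---|
| Overview: TEAE leading to treatment discontinuation | yes | yes | yes | yes |
| General AE table by SOC/PT and TEAE listing | yes, unflagged | yes, unflagged | yes, unflagged | yes, unflagged |
| Treatment-emergent SAEs by SOC/PT | yes, unflagged | no | only if serious | only if serious |
| TEAEs leading to study discontinuation by SOC/PT | **no** | **no** | yes | **no** (if child stays) |
| Reason in disposition table | **no** | **no** | yes | **no** (if child stays) |

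Here, unflagged means that the SAP states no marker for drug having been stopped. On the natural reading of Protocol 4.4, A, B and D are study completers if they attend the last visit. With one such child and no study exits for AEs, the overview row reads 1 and the by-term table reads 0.

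What can be seen about time off drug:

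- SAP 4.6.1 gives the number dosed at each dosing visit, so the number and timing of missed doses are visible.
- The Evaluable Population (SAP 3) requires six full doses and completion through Day 180. SAP 4.1.2 tabulates both completers and membership of each population, so completers minus Evaluable gives, approximately, those who stayed without full dosing.
- No output gives the reason.

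Illustrative size (Protocol 2.2.3.1, the placebo-controlled study):

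- Withdrawn from treatment for an AE on nedosiran: 1/23 = 4.3%, exact 95% CI 0.1% to 21.9%.
- Scaled to 25 participants: 25 × 1/23 = 1.1, with a range from about 0.03 to 5.5.

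The documents do not say whether that participant stayed in the study. The figure therefore concerns AEs that stop drug, not the subset that falls in the gap.

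**The case against.** The strongest reply is that little is lost. Drug-stopping TEAEs are counted in the overview, which is presented by PH type and age group. A related SAE also appears by term in the treatment-emergent SAE table. All TEAEs are listed, and with about one expected case a listing conveys the term and the timing. Protocol 9.4.3.2 promises only that such events will be summarized or listed, and the overview plus listings arguably meet that. Under-6 liver cases with no alternative cause leave the study and are captured; by the synopsis, about 10 + 3 = 13 of the 20 planned completers are aged 5 or younger. Further table specifications are deferred to mock outputs that are not available here.

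Most of this stands, and it rules out several stronger readings:

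- A reader might infer that these AEs are missing from the tables altogether. They are not: they are in the overview, the general table by SOC and PT, and the listings.
- A reader might infer that the number of children off drug, and since when, cannot be seen. SAP 4.6.1 and the Evaluable Population show most of this; only the reason is absent.
- A reader might take the roughly 3 children planned under 1 year and conclude that one case distorts a third of a reported group. The SAP's youngest age group is 0 to under 2 years, so no planned column matches that figure.

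The reply does not remove the mismatch itself. The SAP names study discontinuation explicitly in the by-term item, so unseen mock outputs cannot be assumed to correct it. Cases A, B and D remain outside that table.

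**Conclusion.** The point holds in a limited form. Two outputs in SAP 4.3.1.2.1 that a reader would expect to agree use different events. As a result, AEs that stop nedosiran without study exit are counted but not identified by term, and reasons for stopping drug are not tabulated. The conclusion follows from the text and does not depend on any rate.

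The size is small: probably a handful of children at most. The 1/23 is illustrative only, since it comes from a different study in older participants and does not separate those who stayed from those who left. No efficacy estimate is affected, and no broken protocol promise is established. What is affected is whether the safety tables show what stopped the drug.

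Two assumptions apply: that the triggering findings are recorded as TEAEs, and that the mock outputs do not already contain the missing table.

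**What to change.** In SAP 4.3.1.2.1, change item (2) to *TEAEs leading to permanent discontinuation of study intervention*, by SOC and PT. Give the overview row the same label so that the two agree. Keep TEAEs leading to study discontinuation as a separate row or table. State that this is how the unqualified term in Protocol 9.4.3.2 is read.

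In SAP 4.1.2, add the number and percentage who discontinued study intervention, with reason where collected, and whether they completed Day 180. Given the small numbers, a finer cross-classification would be mostly empty; last dose day can stay in the listing.

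The cost is two table shells. The AE part needs only data that the overview row already requires. Whether non-AE reasons for stopping drug are on the CRF is an assumption to check: Protocol 7.2 says that the reason for leaving the study is recorded, and the documents do not show the same for stopping drug. If those reasons are not collected, report the count and completion status and say so. The change alters no clinical rule.

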4.3.1.2.2 Clinical Laboratory Evaluations

Descriptive summaries for safety laboratory assessments will be presented at each visit starting at baseline. Changes from baseline to each post baseline visit will also be presented for continuous outcomes.

Baseline for safety laboratory assessments will be identified as defined in Section 4b.1.1.2 regardless of whether an evaluation was scheduled, retested, or unscheduled. Since laboratory retests can occur for individual parameters, it will be necessary to define the baseline and all subsequent visit-specific laboratory values individually for each parameter.

In the case where below the limit of quantitation (BLQ) results are observed, and the lower limit of quantification (LLOQ) value is known, the BLQ values will be included in the numeric summary as the reported LLOQ value. In for those lab results reported as ‘<x’ where x is numeric value, descriptive summaries will impute x as the lab result.

The following imputation rules will be applied to safety laboratory results where LLOQ value is unknown:

- If the patient has quantifiable concentrations of that analyte from other study visits, BLQ results will be imputed as ½ of the patient’s lowest concentration for that analyte.
- If the patient does NOT have any quantifiable concentrations of that analyte from other study visits, BLQ results will be imputed as ½ of the lowest concentration of that analyte based on all quantifiable results within the patient’s age group.

By visit summary tables will be presented for each category of data separately. Routine clinical laboratory data will include hematology, clinical chemistry, coagulation parameters, and urinalysis.

Shift tables for baseline to maximum and minimum post baseline grades, based on laboratory normal ranges (below lower limit of normal [LLN], normal, above upper limit of normal [ULN]), will be provided for hematology, coagulation, cytokine, and clinical chemistry parameters. This analysis of extreme value shifts (e.g., maximum and minimum post baseline grades) will be based on all post baseline assessments whether scheduled or unscheduled.

Results of urine pregnancy tests (females only) will be presented in a listing only. Anti-drug antibody tests will be handled similarly.

Data listings for all laboratory results will be generated. Where appropriate, abnormal values (e.g., above the upper limit of normal or below the lower limit of normal) will be identified.

Participant data listings will include the type of visit (e.g., scheduled test, retest, unscheduled), age, sex, laboratory test, test units, laboratory test result, and the laboratory standard normal ranges adjusted as appropriate for age and sex, if available.

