### **Study Intervention Interruption/Discontinuation**

**Study drug must be interrupted** if any of the following criteria are met (applies to participants with normal and elevated transaminases at baseline):

- ALT or AST  $> 8 \times$  ULN
- ALT or AST  $> 5 \times$  ULN for 2 weeks or longer
- ALT or AST  $> 3 \times$  ULN in association with total bilirubin  $> 2 \times$  ULN and/or clinical jaundice or other signs of liver dysfunction (hepatomegaly, pruritus, bleeding, etc).

As children can have LFT elevation from viral infections and medications, an investigation of potential alternative causes (acetaminophen use, EBV, CMV infection, etc) and physical examination should be conducted, and the participant should be closely monitored for clinical progression. **If no alternative etiology is identified, the participant should be discontinued from the study, even if the participant has a normal physical exam.**

If an alternative, reversible cause of transaminase elevation has been identified, and the physical examination is normal the medical monitor should be consulted, and study drug may be resumed after the investigator has confirmed the participant's clinical stability and the transaminases are back to  $< 2 \times$  ULN. Transaminases and bilirubin should be monitored at least weekly for 4 weeks after resuming study drug. **If a protocol defined transaminase elevation ( $> 3 \times$  ULN for participants with normal baseline or  $> 2 \times$  baseline for those**

**with elevated baseline) recurs after re-challenge with the study drug the study drug should be permanently discontinued, regardless of the etiology.**

If a participant lives remote from the study site, local testing may be performed, and the test results reported to the Investigator (along with the reference ranges for the local laboratory).

Participants should be monitored at each study visit and instructed to call the Investigator for new or worsening symptoms of clinical hepatitis and/or liver dysfunction. Both symptoms and calls should be captured in dedicated eCRFs.

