4.1.1.2 Baseline

For all endpoints (except spot urinary oxalate-to-creatinine ratio and annualized stone events rate), the last non-missing observation recorded prior to the first dose of study intervention will be used as the baseline observation for all calculations of change from baseline.

For assessments where the time is not collected (like QoL questionnaires), the last observation recorded prior or during the day of the first dose will be considered as baseline.

For spot urinary oxalate-to-creatinine ratio (including spot urinary oxalate and creatinine measurements), the average of all available spot urine samples (retest samples will be used if available) collected at screening will be used as baseline value.

For annualized stone events rate, baseline will be the number of stone events observed over the past 12 months prior to screening.

Any measure assessed after the date/time of the first dose will be considered as post baseline assessments.

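### For a safety result below an unknown quantification limit, the SAP can build a child's baseline from on-drug values, which can understate the change from baseline

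*SAP*

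**What the plan says.** SAP 4.3.1.2.2 treats BLQ safety results in two tiers.

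- **Limit known.** Where the LLOQ is available, "the BLQ values will be included in the numeric summary as the reported LLOQ value". For a result given as '<x', "descriptive summaries will impute x as the lab result".
- **Limit unknown.** "The following imputation rules will be applied to safety laboratory results where LLOQ value is unknown". The first rule begins "If the patient has quantifiable concentrations of that analyte from other study visits" and continues: "BLQ results will be imputed as ½ of the patient’s lowest concentration for that analyte". If the child has no quantifiable value at any other visit, the substitute is "½ of the lowest concentration of that analyte based on all quantifiable results within the patient’s age group".

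SAP 4.1.1.2 defines the laboratory baseline: "the last non-missing observation recorded prior to the first dose of study intervention will be used as the baseline observation". SAP 4.3.1.2.2 then plans by-visit values, by-visit changes from baseline, and shift tables from baseline to the post-baseline maximum and minimum in three classes (below LLN, normal, above ULN). It does not say whether the shift tables class a BLQ result by its imputed value or by its BLQ status. Change from baseline in clinical laboratory tests is a named secondary safety endpoint (SAP 1.1.1 and 4.3.1.2).

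**The concern.** With an unknown limit, the substitute may come from any other visit, including visits after dosing. If both Screening and Day 1 pre-dose are BLQ, the only donors left are on-drug results. The baseline is then computed from the values that it is meant to be compared with, and the larger those values are, the higher it becomes. It has no ceiling, although the true value is known to lie below the assay limit.

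The two unknown-limit rules also treat children unequally. A child who stays undetectable throughout receives half of the age-group minimum. A child in the same age group who becomes quantifiable on drug receives half of his or her own minimum, which cannot be lower. The child with the signal thus gets an equal or higher baseline, and the bias runs towards no change.

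About 20 completers are expected (SAP 5) in four age groups (SAP 4.1.2), or 20/4 = 5 per group on average before splitting by PH type. One affected child is then 1/5 = 20% of an average cell.

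**Working it through.** The documents give no figure on this point, so there is none to reproduce. They also give no LLOQs, reference limits or BLQ frequencies, so the profiles below are assumed and only the rule comes from the SAP.

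**Notation (in multiples of ULN).** m = the child's lowest quantifiable value; X = the value at a visit; b = true baseline, with 0 ≤ b < LLOQ. I take a BLQ result as non-missing for the baseline definition.

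**Formulas.**
- Imputed baseline = m/2.
- Reported change = X − m/2; true change = X − b.
- Share kept = (X − m/2)/(X − b).
- The imputed baseline is above the true one whenever m > 2b, and is classed above ULN only when m > 2 x ULN.

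**General case, b = 0 and X = k x m.** The share kept is (k − 0.5)/k: 50% at k = 1, 75% at k = 2, 83% at k = 3, 90% at k = 5.

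**Assumed profiles.** Screening, Day 1 and six on-drug visits. Screening and Day 1 are BLQ except in the last row. The lower limit of normal is 0. LLOQs of 0.05, 0.10 and 0.20 x ULN were tried; the ranges shown are for b from 0 to 0.20, the widest.

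| On-drug values | Imputed baseline | Reported maximum rise | True maximum rise | Share kept | Shift if imputed value is used |
|---|---|---|---|---|---|
| Flat 0.8 | 0.40 | 0.40 | 0.60–0.80 | 50–67% | normal to normal (correct) |
| Flat 1.5 | 0.75 | 0.75 | 1.30–1.50 | 50–58% | normal to high (correct) |
| Flat 3 | 1.50 | 1.50 | 2.80–3.00 | 50–54% | high to high (true: normal to high) |
| One value of 1.8, rest BLQ | 0.90 | 0.90 | 1.60–1.80 | 50–56% | normal to high (correct) |
| One value of 6, rest BLQ | 3.00 | 3.00 | 5.80–6.00 | 50–52% | high to high (true: normal to high) |
| 0.3, 0.6, 1, 2, 3, 4 | 0.15 | 3.85 | 3.80–4.00 | 96–101% | normal to high (correct) |
| 1, 2, 3, 4, 5, 6 | 0.50 | 5.50 | 5.80–6.00 | 92–95% | normal to high (correct) |
| Screening 0.2, Day 1 BLQ, then flat 3 | 0.10 | 2.90 | 2.80–3.00 | 97–104% | normal to high (correct) |

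**By-visit tables.** At the visit where X = m, the reported change is always m/2. For the 1-to-6 profile that is 0.50 against a true 0.80 to 1.00, so roughly half to five-eighths is kept, even though the peak is nearly intact. For the 0.3-to-4 profile it is 0.15 against 0.10 to 0.30, so the rule may understate or overstate.

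**Comparison with a fixed substitute.** Setting the baseline to the LLOQ or half of it (0.05 to 0.20 x ULN) gives a rise of 2.80 to 2.975 for the flat-3 profile, not 1.50, and 5.80 to 5.975 for the single value of 6, not 3.00. Both shifts are then normal to high.

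**The case against.** **Scope.** The rule reaches only results with neither a known LLOQ nor a '<x' number. Protocol 10.2 sends the listed safety tests to a central laboratory, which should know its limits, and the documents name no analyte where the limit is unknown. A quantifiable Screening value caps the imputed baseline at half of that value. All of this stands, and it makes the point a small one. It does not make the rule correct where it applies, and the SAP itself provides for the case.

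**Other safeguards.** All laboratory results are listed, raised values stay in the by-visit summaries, and Protocol 10.6 has the central laboratory send real-time liver alerts. So a reader should not infer that a safety signal would go unnoticed; what can be wrong is the tabulated change and possibly the shift.

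**Stronger readings that the documents do not support.**
- *That a rise is generally halved.* This needs a value close to m and a true baseline near zero. The maximum of both progressive profiles is 92% or more intact.
- *That the normal-to-high shift is generally lost.* This needs m above 2 x ULN and shift tables built on imputed values, which the SAP leaves open.
- *That the known-limit and unknown-limit rules contradict each other.* Their conditions are mutually exclusive. They differ in quality but do not conflict.
- *That local liver testing (Protocol 10.6) supplies BLQ baselines.* That testing follows up raised values during the study, so it is neither pre-dose nor likely to be BLQ. Protocol 8 does let routine pre-consent results serve as baseline, but only on protocol terms, and a later pre-dose Day 1 result would replace them.

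**Conclusion.** The point holds as a narrow defect in a stated rule. When the LLOQ is unknown and all pre-dose results for an analyte are BLQ, the baseline is derived from on-drug values. The reported change can then be understated by up to about half at visits near the child's lowest quantifiable value if the true baseline is near zero, and by much less at the peak of a progressive rise. A normal-to-high shift can be lost only if the lowest quantifiable value exceeds 2 x ULN and the shift tables use imputed values.

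The conclusion rests on reading a BLQ result as non-missing for the baseline definition. The sizes come from assumed profiles and limits. Few records are likely to be affected, all safety summaries are descriptive, and no efficacy result is touched. It is worth correcting because the error favours the drug in a named secondary safety endpoint and the correction is cheap.

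**What to change.** Replace both unknown-limit rules in SAP 4.3.1.2.2 with the following:

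1. Obtain the LLOQ from the laboratory and apply the existing known-LLOQ rule.
2. Failing that, use one fixed substitute per analyte and laboratory, the same at every visit. It could be based on the lowest quantifiable value that the laboratory reported across all participants. It must never be derived from the individual child's own post-dose values; if no other participant has a quantifiable result there, keep the result as BLQ in the listing and do not compute a change.
3. State that a BLQ result is never classed as above ULN in the shift tables.

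Do not cap the substitute at the lower reference limit. That would force zero where the limit is zero, and would be wrong where the assay's LLOQ lies above it.

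The cost is a short SAP edit and possibly one laboratory query. The pooled value in step 2 may itself come from a post-dose sample, but it no longer moves with the affected child's own results.

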### **2.3.5. Overall Benefit:Risk Conclusion**

At present, no therapies are approved by regulatory authorities for the treatment of patients with PH2 or PH3. Lumasiran, a treatment for PH1, is approved in a limited number of countries, including the European Union. A number of supportive therapies are also used in an attempt to mitigate some of the effects of the disease, but affected patients are at considerable risk of serious complications like renal stones, nephrocalcinosis, renal failure, and systemic tissue damage due to oxalate deposition. Combined liver-and-kidney transplantation is the only causative therapy but is associated with short- and long-term complications as well.

Thus far nedosiran treatment has shown potential benefit to reduce or prevent the excess oxalate production in the liver. If sustained, this could eliminate the need for a liver transplantation.

The potential risks with nedosiran include low elevations of liver function tests, muscle damage, and stimulation of pattern recognition receptors (e.g., Toll-like receptors) leading to cytokine release, inflammation, and ISRs. These risks can be monitored and should be reversible after drug discontinuation. The results from the completed study, DCR-PHXC-101, demonstrate the potential for nedosiran to bring patients into a near-normal or normal range of their 24-hour Uox values. Continuous risk-benefit assessments will be conducted by the Sponsor, the Medical Monitor of the CRO, and the SRC on an ongoing basis.

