**Diagnostic assessments**

9. Liver function test (LFT) abnormalities: ALT and/or AST >  $1.5 \times \text{ULN}$  for age and gender

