4.1.1.5 Analysis Visit Windows

By-visit summaries will be based on electronic case report form (eCRF)-defined nominal visits.

In general, analysis of all variables for this study will use the nominal visit or time point as collected on the electronic case report form (eCRF) and/or database. Scheduled visits will be selected over unscheduled visits.

For those participants who discontinue early from the study and the Early Termination (ET) visit satisfies the following condition:

- 20 days ≤ the date of ET - the date of the last visit before ET + 1 ≤ 40 days

then the ET visit will be mapped to the next scheduled visit. Otherwise, the ET will not be mapped into any analysis visits.

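### The SAP's laboratory tables do not count ALT/AST on the scales the protocol's liver rules use, so a rise that triggers interruption or discontinuation can be tabulated as no shift

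*SAP*

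**What the plan says.** Protocol 2.3.5 states: "The potential risks with nedosiran include low elevations of liver function tests, muscle damage", among other potential risks. Exclusion criterion 9 (Protocol 5.2) reads "Liver function test (LFT) abnormalities: ALT and/or AST" above 1.5 x ULN for age and gender, so a child at or below that level may enter. Appendix 6 (Protocol 10.6) then sets its actions as follows.

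- Age 6 and over, normal baseline: close monitoring above 3 x ULN. Discontinuation criteria include above 8 x ULN, above 5 x ULN for more than 2 weeks, and above 3 x ULN with total bilirubin above 2 x ULN or INR above 1.5.
- Age 6 and over, raised baseline: close monitoring above 2 x baseline. Discontinuation above 5 x baseline when baseline is below 2 x ULN.
- Under 6, any baseline: interruption criteria include above 8 x ULN, above 5 x ULN for 2 weeks or longer, and above 3 x ULN "in association with total bilirubin" above 2 x ULN and/or clinical signs of liver dysfunction.

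The laboratory section of the SAP (4.3.1.2.2) has three outputs. First, "Descriptive summaries for safety laboratory assessments will be presented at each visit starting at baseline", with changes from baseline. Second, "Shift tables for baseline to maximum and minimum post baseline grades, based on laboratory normal ranges (below lower limit of normal [LLN], normal, above upper" (three levels in all, the top one being any value over ULN). These tables "will be provided for hematology, coagulation, cytokine, and clinical chemistry parameters" and use all post-baseline assessments, scheduled or not. Third, "Data listings for all laboratory results will be generated", with out-of-range values flagged where appropriate. For by-visit tables, SAP 4.1.1.5 adds, as a general rule: "Scheduled visits will be selected over unscheduled visits".

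**The concern.** In the shift table, everything above ULN is one category. That category holds values the protocol ignores, values it monitors closely, and values at which it interrupts or discontinues treatment. A child who enters already above ULN cannot shift upward, however large the rise. By-visit summaries treat each analyte separately, so they cannot show whether a raised transaminase and a raised bilirubin occurred in the same child.

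At stake is a basic safety result. Change in clinical laboratory tests is a secondary safety endpoint, and the trial extends dosing down to birth. The SAP plans no count of how many children reached the protocol's own liver action levels, or had the combined abnormality.

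**Working it through.** The plan gives no figure on this point to reproduce. The check applies the SAP's shift rule and the Appendix 6 rules to the same child. The pair 1.4 and 9 x ULN is my illustration, with 1.4 x ULN taken as the SAP baseline value.

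**Eligibility.** Exclusion applies above 1.5 x ULN. 1.4 is below 1.5, so the child may enter, with a raised baseline.

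**Appendix 6, age 6 and over, raised baseline.** 9 / 1.4 = 6.43 x baseline. The criterion is above 5 x baseline, here 5 x 1.4 = 7.0 x ULN, with baseline below 2 x ULN. Both parts hold, so the discontinuation criterion is met.

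**Appendix 6, under 6.** 9 is above 8 x ULN, so the interruption criterion is met.

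**SAP shift table.** A value above 1 x ULN is classed as above ULN.

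| Baseline (x ULN) | Peak (x ULN) | Shift-table cell |
|---|---|---|
| 1.4 | 1.45 | above ULN to above ULN |
| 1.4 | 9 | above ULN to above ULN |
| 0.8 | 1.05 | normal to above ULN |
| 0.8 | 9 | normal to above ULN |

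Rows 1 and 2 are indistinguishable, and so are rows 3 and 4. The loss of information therefore does not depend on a raised baseline.

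**Unscheduled repeats.** Appendix 6 asks for repeat testing within 48 to 72 hours once ALT/AST passes 3 x ULN or, with a raised baseline, 2 x baseline (2 x 1.4 = 2.8 x ULN here). Chemistry is scheduled on Days 1, 30, 60, 90, 120, 150 and 180. If a scheduled draw is the trigger, its value stays in the by-visit table. A higher value on the repeat can be left out, because scheduled visits take precedence. The repeat does enter the shift table, but in the same cell.

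**Combined abnormality.** ALT, AST, bilirubin and INR are summarised and shifted parameter by parameter. Separate counts cannot show whether two abnormalities occurred in one child.

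**With a threshold table.** The child in row 2 would count in the above 3, 5 and 8 x ULN rows and in the above 2 and 5 x baseline rows. That is 1 of 20 (5%) on the planned completers, or 1 of 25 (4%) on the planned enrolment.

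**The case against.** The strongest reply is that the information is not lost. Where the SAP spells out its descriptive statistics (4.2.2, 4.3.1.1, 4.4), they include median, minimum and maximum. If the same set is used for laboratory data, a 9 x ULN value at a scheduled visit appears as the maximum of its age group. Every result is listed with its visit type and, where available, the age- and sex-adjusted normal range. With about 25 children, a reader could count by hand. Clinically significant results become adverse events, and TEAEs leading to treatment discontinuation are tabulated. The SAP also leaves unspecified table details to the mock TFL, which is not available here.

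Much of this stands, and it rules out several readings that a reader might infer:

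- That liver tests are reported by means alone. The SAP says descriptive summaries, and it also plans listings.
- That repeat tests always vanish. They can be absent from by-visit tables, but they remain in the shift tables and listings.
- That liver injury could go unnoticed. Appendix 6 provides real-time central laboratory alerts, and the SRC reviews safety data.
- That the example carries over to CK. CK has no entry ceiling and no Appendix 6 cut-point, so the mismatch shown here does not arise for it.

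The reply does not supply the missing count. A listing is not a summary. A maximum in laboratory units is not scaled to each child's ULN and cannot be paired with bilirubin. Adverse event reporting depends on investigator judgement, the AE overview has no line for interruption (the first action under 6), and no liver event is an AESI. The SAP does specify graded thresholds in its own text for QT and QTcF, with extreme values taken from all assessments (4.3.1.2.4), so leaving the liver equivalent to the mock TFL would be out of keeping with its own practice.

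**Conclusion.** The point holds for the SAP text. No table it describes uses multiples of ULN, multiples of baseline, or ALT/AST combined with bilirubin or INR, although Appendix 6 acts on all of these. A permitted baseline of 1.4 x ULN with a peak of 9 x ULN meets an action criterion in both age bands and is tabulated as no shift. This is a gap in planned summary reporting that should be closed. It is not evidence of a monitoring failure, and it says nothing about whether the Appendix 6 levels are right.

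The conclusion assumes that the mock TFL does not already contain such a table. The documents give no expected frequency for these elevations, so I put no figure on how many children would be affected.

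**What to change.** In SAP 4.3.1.2.2, add one table by the existing age groups, which already split at 6 years. Use all scheduled and unscheduled post-baseline values and the age- and sex-specific ULN. Count:

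1. children whose peak ALT or AST exceeded 3, 5 and 8 x ULN;
2. children with ALT or AST above 3 x ULN together with total bilirubin above 2 x ULN or, at age 6 and over as in Appendix 6, INR above 1.5, stating how the values are paired in time;
3. among children with raised baseline transaminases, those with ALT or AST above 2 x and above 5 x baseline.

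All cut-points are already in the protocol, and no treatment rule changes. The table counts laboratory levels only. The 2-week duration and the symptom or clinical-sign criteria would still need case review. No CK threshold is needed; if wanted, peak CK can be described as a multiple of ULN.

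The cost is SAP wording and a little programming on data already collected. Cells will be very small, so the counts should be read alongside the listings.
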